2.2. Background

BP is the most common autoimmune blistering skin disease, with an estimated annual incidence of 2.4 to 23 cases per million individuals. However, among people >80 years of age, the incidence ranges from 190 to 312 cases per million individuals. ^{6,7} The disease has a poor prognosis, which is directly attributable to the advanced age of the patient population and the comorbidities that can be present in this population. A recent meta-analysis calculated that the relative risk of death among patients with BP during a 1-year period is 2.93 times greater that of the general worldwide population (adjusted for age and sex). Studies examining the all-cause mortality among patients with BP beyond 1 year have reported higher death rates in the first year (20% to 27%) than in subsequent years (9% to 16%). The main causes of death were infections and cardiovascular disorders, which are attributable to both the older age of patients with BP and their use of corticosteroids and/or immunosuppressants.

In BP, the disruption of the dermal-epidermal junction by pathogenic autoantibodies results in large, tense bullae on the skin, progressing to epidermal erosion, crusting, and urticarial plaque formation. Without treatment, BP ultimately progresses to life-threatening complications, including (but not limited to) severe infections, functional impairment of vital organs, and iatrogenic conditions.

Corticosteroids (either topical or oral) are currently the first-line therapy for the treatment of patients with BP. For BP that is either localized or mild/moderate in severity, medical authorities recommend application of high-dose TCS of strong potency (such as clobetasol propionate at doses from 20 to 40 g/day). ^{9,10} Unfortunately, the use of TCS at such high doses results in a substantial systemic absorption and severe skin atrophy. ¹¹

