3.4.2 Derivation rules

Based on their start and stop dates, therapies will be allocated to each phase and period during which the participant received the therapy.

Therapies/procedures with (partially) missing dates will be allocated to each phase/period unless the available parts of the therapy/procedure start or stop date provide evidence not to do so.

Based on their start and stop date, therapies and procedures will be allocated into one or both of the following categories:

- Prior: any therapy/procedure that strictly started before the first IMP.
- Concomitant: any therapy/procedure that was taken on or after the first IMP.

A medication that started before the first IMP and continued during the study will be classified as both prior and concomitant.

Therapies/procedures with (partially) missing dates will be allocated to each category unless the available parts of the therapy/procedure start or stop date provide evidence not to do so.

Under certain conditions (see CTP section 6.8.3), participants will discontinue IMP treatment and may start rescue therapy. Rescue therapy may include OCS, TCS, immunosuppressants, tetracyclines with or without nicotinamide, dapsone, or IVIg.

Intercurrent events (ICE) of disallowed therapies that may influence efficacy are defined as any of the following therapies (and that are not prescribed as rescue therapy):

- Immunosuppressants or dapsone at therapeutic doses for at least 4 weeks in total
- IVIg /SCIg at immunomodulating dose (≥1 g/kg/month)
- Tetracyclines at therapeutic dose for at least 2 weeks in total
- Rituximab or other anti-CD20 biologics, at least 1 infusion
- Plasma exchange or Immunoadsorption, at least 1 procedure
- IV or IM corticosteroids

At least 1 administration, any dose, from week 28 to 36 (i.e., during the 8-week period required to confirm CR off OCS therapy) or

At any time before week 28 in any of the 3 following situations:

- More than 60 mg/day of prednisone or prednisone equivalent dose for 3 consecutive days
- More than 40 mg/day of prednisone or prednisone equivalent dose for 4 consecutive days
- More than 7 days in total
- Any interventional study drugs under development for BP
- Very potent topical corticosteroids (TCS) for 7 consecutive days or 14 days in total

Note: if dose is missing and/or period of intake cannot be derived, it is still considered an intercurrent event.

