4.1.2.1 ESTIMAND ANALYSIS

- Population: adult participants with newly diagnosed or relapsing BP, regardless of whether the participant is naïve to treatment or has previously received treatment. Participants will be receiving concurrent therapy of oral prednisone (or equivalent OCS); therefore, candidates who have a known contraindication to OCS will be excluded from study participation (exclusion criterion 4).
- Subject level variable: being in CR while receiving efgartigimod PH20 SC or placebo and have been off OCS therapy for ≥8 weeks (CRoff) at week 36.
- Main intercurrent events:
 - 1. Intercurrent treatments before week 36 (see appendix 9.1)
 - Immunosuppressants or dapsone at therapeutic doses for at least 4 weeks in total
 - IVIg /SCIg at immunomodulating dose (≥1 g/kg/month)
 - Tetracyclines at therapeutic dose for at least 2 weeks in total
 - Rituximab or other anti-CD20 biologics, at least 1 infusion
 - Plasma exchange or Immunoadsorption, at least 1 procedure
 - IV or IM corticosteroids

At least 1 administration, any dose, from week 28 to 36 (i.e., during the 8-week period required to confirm CR off OCS therapy) or

At any time before week 28 in any of the 3 following situations:

- More than 60 mg/day of prednisone or prednisone equivalent dose for 3 consecutive days
- More than 40 mg/day of prednisone or prednisone equivalent dose for 4 consecutive days
- More than 7 days in total

- Any interventional study drugs under development for BP
- Very potent TCS for 7 consecutive days or 14 days in total
- 2. Discontinuation of IMP before week 36 due to lack of efficacy
- 3. Death before week 36

Details on the derivation of intercurrent treatments are provided in appendix 9.1.

Population-level summary: the odds ratio (with 95% confidence interval [CI])
under efgartigimod PH20 SC in combination with concurrent OCS therapy
versus PBO PH20 SC in combination with concurrent OCS therapy.

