A participant is considered as CRmin at week 36 when the reported disease status at week 36 is 'CR while receiving minimal OCS therapy for at least 8 weeks' or 'CR while being off OCS therapy for at least 8 weeks', or else when the reported disease status at week 36 belongs to a sequence of episodes with disease statuses 'CR while receiving minimal OCS therapy for less than 8 weeks *or* for at least 8 weeks' and' CR while being off OCS therapy for less than 8 weeks *or* for at least 8 weeks', having

SGS	Statistical Analysis Plan		
ARGX-113-2009	Final and Interim Analysis	Final 4.0 of 04NOV2024	

started at least 56 days earlier (and for which within these 56 days the disease status provides evidence that the participant remained in CR and the minimal OCS therapy was maintained).

The same approach for handling the main ICEs (composite strategy), for handling rescue therapies and for handling missing data, as suggested for the primary analysis, will be applied.

5) The Itch NRS is measured over time and changes from baseline in the 24-hour average itch score will be analysed. A 'treatment policy' approach will be applied by ignoring the main ICEs. For participants who received rescue therapy, only assessments prior to or on the start date of rescue therapy will be included in the analysis.

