11) Time from CRoff onset to Relapse, calculated only in participants with CRoff as the difference between the first date of relapse and the first date CRoff was achieved. Similar calculations and censoring rules are applied as for 'time from CDA to Relapse'.

Time from CR onset to Relapse will be analysed in a similar way as 'time to CRmin'.

- 12) NCOD as calculated for the different subperiods. NCOD from CDA/CR onset until relapse will only be analysed in participants with CDA/CR respectively. Same analysis will be performed as for the primary estimand of the key secondary parameter with ICEs handled according a 'while on treatment' strategy.
- COD will be calculated for the on IMP treatment period and the subperiods mentioned before. Only descriptive statistics will be presented.
- 13) Changes from baseline at week 36 in the 24-hour worst Itch NRS score will be analysed in the same way as for the 24-hour average itch score in the key secondary analysis.
- 14) Proportion of participants who received rescue therapy before week 36. A 'treatment policy' approach will be applied by ignoring main ICEs. Same CMH model as proposed for the primary endpoint.
- 15) ABQOL (17 items), EQ-5D-5L (5 dimensions) and DLQI (10 items) are assessed by the investigator at baseline, Week 12, Week 26 and at Week 36/ETD/ESD. Frequency tabulations will be provided for the percentages of participants within each outcome of QoL questionnaire items. Additionally cumulative percentages (starting with the best outcome result) will be calculated. A 'treatment policy' approach will be applied by ignoring main ICEs. For participants who received rescue therapy, only assessments prior to or on the start date of rescue therapy will be considered.
- 16) EQ-5D-5L VAS score and DLQI score are assessed by the investigator at baseline, Week 12, Week 26 and at Week 36/ETD/ESD. A total ABQOL score is calculated as the sum of all 17 items score 0 to 3 with higher score indicating worse condition. Missing items are imputed with the average score of the present items if at least half (9) of the items are present. The total score is rounded to the highest integer. A 'treatment policy' approach will be applied by ignoring main ICEs. For participants who received rescue therapy, only assessments prior to or on the start date of rescue therapy will be considered.

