6. CHANGES TO THE PLANNED ANALYSIS

6.1 CHANGES NOT COVERED BY PROTOCOL AMENDMENTS BEFORE DATABASE LOCK

1.) The protocol specifies the NCOD calculation as:

Normalized cumulative OCS dose (NCOD) will be calculated normalized by weight and by number of days in study. The following formula will be adopted to calculate NCOD for each participant.

 $NCOD = \frac{\textit{Cumulative Dose of OCS from baseline to the week 36 visit}}{(\textit{Weight of the patient at baseline})} \times (\textit{number of days in study})$

Instead of the weight at baseline, it was chosen to use the most recent weight assessment instead. NCOD (mg/kg/day) is calculated for different periods as [the sum of (equivalent doses taking into account daily dose frequency)/(body weight in kg)]/(period duration in days) with body weight of visit closest before or at each start of prednisone equivalent medication instead of using weight at baseline.

- 2.) This SAP defines intercurrent medications in more detail than the protocol:
 - Immunosuppressants or dapsone at therapeutic doses for at least 4 weeks:
 - Doses considered as therapeutic dose are specified in SAP appendix
 9.1
 - Only considered as intercurrent medication if administered in the last 12 weeks before Week 36
 - Tetracyclines at the apeutic dose for at least 2 weeks:
 - Doses considered as therapeutic dose are specified in SAP appendix
 9.1
 - Only considered as intercurrent medication if administered in the last 10 weeks before Week 36
 - Very potent TCS with a weekly dose >20 g for 1 week:
 - Since the dose of TCS cannot be derived from the eCRF data, very potent TCS is considered as intercurrent medication when it is applied for 7 consecutive days or 14 days in total.
- 3.) Per protocol, death before week 36 is not considered as main intercurrent event in the efficacy analysis. It is added as main intercurrent event in this SAP.

[figure not shown]

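### Death is a main intercurrent event in the SAP, but the rescue-therapy endpoint and alpha-controlled itch ignore main intercurrent events with no exception for death

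*SAP*

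**What the plan says.** The third main intercurrent event in SAP 4.1.2.1 is "Death before week 36". SAP 6.1 records that the protocol did not treat death this way in the efficacy analysis, and says: "It is added as main intercurrent event in this SAP".

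Two endpoints are then told to disregard main intercurrent events:

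- **Rescue therapy** (SAP 4.1.4 item 14, not alpha controlled): "Proportion of participants who received rescue therapy before week 36. A 'treatment policy' approach will be applied by ignoring main ICEs". The test is the CMH model of the primary endpoint. This section is analysed on the full analysis set. SAP 2.4.1 puts all participants of the analysis set in the denominator of frequency tables.
- **24-hour average itch** (SAP 4.1.3.1 item 5, alpha controlled in Part B): "A 'treatment policy' approach will be applied by ignoring the main ICEs". Assessments after the start of rescue are left out. SAP 4.1.3.2 estimates the week-36 least squares mean with an MMRM.

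Elsewhere the SAP deals with death explicitly. The primary endpoint and key secondary endpoints 2 to 4 use a composite strategy in which death is failure. The supplementary treatment-policy analysis of the primary endpoint (SAP 4.1.2.2) ignores the other main intercurrent events but still scores death as non-response, and the multiple-imputation note in SAP appendix 9.3 repeats this.

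**The concern.** A treatment-policy strategy uses the outcome observed after the event. After death there is none, so ignoring death leaves the value to be settled by default.

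For item 14 the default is a good result. Someone who dies without rescue has no rescue record and falls in the rescue-free group. Deaths remove people who might later have needed rescue, so an arm with more deaths tends to look better on rescue avoidance.

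For itch, scores after death are treated like any other missing scores. The week-36 mean then describes a population in which nobody dies. Itch is in the fixed sequence, and SAP 1.4.3.2 orders the key secondary endpoints by their interim p-values, so itch could be tested directly after the primary endpoint. A confirmatory claim should rest on an estimand that is defined for participants who die.

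Death is not a remote event in this disease. Protocol 2.2 cites first-year mortality of 20% to 27%, and protocol 9.3.3.3 acknowledges high mortality in the study population.

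**Working it through.** The documents give no planned rescue rate, itch effect or death rate, so there is no figure of the plan's own to reproduce. Rates below are assumptions unless a source is named.

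**1. How common could death be?** Inputs: 20% to 27% in year 1 (protocol 2.2), 36 weeks = 252 days, constant hazard assumed.
- 1 − (1 − 0.20)^(252/365) = 14.3%
- 1 − (1 − 0.27)^(252/365) = 19.5%
- At 60 per arm, that is about 9 to 12 deaths. This is an upper guide, because entry requires a Karnofsky score of at least 60%.

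**2. Rescue, simple counts.** Assume 60 per arm, 30% of survivors rescued in both arms, and 6 versus 12 unrescued deaths.
- As the SAP is written: 54 × 0.30 / 60 = 16.2/60 = 27%, against 48 × 0.30 / 60 = 14.4/60 = 24%.
- Death counted as an event: (16.2 + 6)/60 = 37%, against (14.4 + 12)/60 = 44%.

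The first comparison favours the arm with twice the deaths; the second reverses it. A second example has 15 versus 21 rescued and 9 versus 3 unrescued deaths. The SAP rule gives 25% versus 35%, an apparent benefit. The composite gives 24/60 versus 24/60, or 40% in each arm.

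**3. Rescue, competing risks.** Let r and d be the 36-week probabilities of rescue and death, each in the absence of the other, with hazards h_r = −ln(1 − r) and h_d = −ln(1 − d).
- Observed rescue = h_r/(h_r + h_d) × [1 − (1 − r)(1 − d)]
- Rescue or death = 1 − (1 − r)(1 − d)

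The rescue hazard is the same in both arms; d is 5% versus 20%.

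| r | Observed rescue | Rescue or death |
|---|---|---|
| 20% | 19.5% vs 18.0% | 24.0% vs 36.0% |
| 30% | 29.3% vs 27.1% | 33.5% vs 44.0% |
| 40% | 39.1% vs 36.2% | 43.0% vs 52.0% |

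The higher-mortality arm shows 1.5 to 2.9 points less rescue, but 9 to 12 points more rescue-or-death.

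**4. Itch, what the model estimates.** A large-sample simulation used the 13 visits, an ANTE(1) structure, an assumed week-36 mean change of about −4 with SD 2.2, and 5% to 20% deaths. The model returned −3.98 whatever the death rate. The mean among survivors was −3.98 when death was unrelated to itch, and −4.01 to −4.11 when worse itch raised the risk of death.

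**5. Itch, a composite for comparison.** Assume survivor changes of −4 versus −3, death unrelated to itch, and zero change for those who die.
- MMRM difference: −4 − (−3) = −1.0.
- Deaths 8% versus 3%: −4 × 0.92 + 3 × 0.97 = −3.68 + 2.91 = −0.77.
- Deaths 3% versus 8%: −4 × 0.97 + 3 × 0.92 = −3.88 + 2.76 = −1.12.

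The composite moves either way, depending on which arm has more deaths.

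**The case against.** **The main intercurrent event list belongs to the primary estimand.** One could argue that death is not meant in item 14 or itch. But SAP 6.1 adds death for the efficacy analysis generally. The cumulative-steroid endpoint restates its own list, while these two endpoints do not. Even on the narrower reading neither endpoint has a death rule, and the default results are the same.

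**Unrescued deaths might be coded missing.** SAP 2.4.1 would then drop them from the percentages. In the example above this gives 16.2/54 = 30% versus 14.4/48 = 30%, a comparison of survivors. But an instruction to ignore death gives no ground for coding it missing, and item 14 has no missing-data rule.

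**The distortion in raw rescue is small, and deaths are tabulated separately.** This stands in part. In the first example it amounts to 16.2 versus 14.4 participants, and most of the 37% versus 44% contrast comes from adding the deaths to the outcome. A separate safety table would show an imbalance but would not correct the CMH test.

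**The itch numbers compare two estimands.** This stands. The −0.77 arises from assigning zero change to deaths, and against survivor means the shift is slight.

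**Two stronger readings are tempting but unsupported.** A reader might infer that participants who withdraw unrescued are also scored as rescue-free by this rule. Withdrawal is not a main intercurrent event, so the quoted sentence does not govern it, and the SAP does not say how such participants are coded. A reader might also infer that prohibited therapy is wrongly left out of item 14, since SAP 3.4.2 limits that category to treatments "and that are not prescribed as rescue therapy". But protocol 6.8.3 places rescue after stopping IMP, and item 14 counts that. Merging the two would redefine the endpoint.

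**Conclusion.** The gap is real for death on both endpoints. It comes from a stated rule that conflicts with the SAP's own handling of death in the treatment-policy analysis of the primary endpoint.

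- **Rescue:** followed as written, an unrescued death is scored as the favourable outcome. Raw rescue is distorted by about 1.5 to 3 points in the illustrations, and the comparison can change direction once death counts. The endpoint is not alpha controlled.
- **Itch:** the endpoint is alpha controlled, but the demonstrated problem is one of meaning: the estimate describes a world without deaths. A material numerical bias has not been shown.

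A reader might infer that the rule favours efgartigimod. The documents do not support that. The direction depends on deaths by arm, which are not given, and every death split used here is an assumption. The cited mortality is for patients with the disease in general, and trial mortality may be lower.

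**What to change.** Carry the death exception of SAP 4.1.2.2 over to both endpoints before unblinding.

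- **SAP 4.1.4 item 14:** count death before week 36 without prior rescue as an event in the CMH comparison. Report the raw rescue percentage beside it, so that the protocol's endpoint stays visible.
- **SAP 4.1.3.1 item 5:** exempt death from the instruction to ignore main intercurrent events and name a strategy for it. One option is a composite with no improvement from baseline at week 36 for those who die, at least as a prespecified supplementary analysis beside the MMRM. State how visits between death and week 36, and deaths after rescue, enter that analysis.

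The cost is a few sentences and a short derivation, with no new data and no design change. The downside is that the composite rescue percentages will be noticeably higher than the raw ones if deaths are common: 27% becomes 37%, and 24% becomes 44%, in the first example.

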6.8.3. Rescue Therapy

Participants will discontinue IMP and may start rescue therapy if any of the following occur:

- The participant fails treatment with IMP (defined in Section 4.1.3)
- The participant relapses twice
- The participant presents with steroid toxicity (or any severe AE determined by the investigator to be related to OCS therapy)

Participants reporting any of the events mentioned above will permanently discontinue IMP (Section 7.1.1).

Rescue therapy may include OCS, TCS, conventional immunosuppressants (eg, azathioprine, cyclophosphamide, methotrexate, mycophenolate mofetil), tetracyclines with or without nicotinamide, dapsone, or IVIg. As described in Section 6.8.2, these treatments are permitted as rescue therapy following discontinuation of IMP.

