9.3.3.2. Analysis of Other Secondary Endpoints

Other secondary endpoints (which are not subject to alpha control) are listed in Table 3 and Table 4; these have been selected to evaluate other aspects of the effects of efgartigimod PH20 SC in participants with BP, including its safety/tolerability, health impact, QoL, PK/PD, and immunogenicity. Additionally, this study includes endpoints to evaluate whether participants (and/or their caregivers) can competently (self-)administer efgartigimod PH20 SC.

These endpoints are not subject to multiplicity correction, and their analyses are purely descriptive.

Time to CDA and CR will be tested using a stratified Gehan-Wilcoxon test. The other time to event endpoints will be tested using a stratified log-rank test.

All continuous secondary endpoints (such as the C-GTI and QoL instruments) will be analyzed using a mixed-effect model for repeated measures.

Descriptive statistics will be provided for self-administration training, PD (total IgG serum levels and the anti-BP180 and anti-BP230 antibodies), incidence of ADA and NAb against efgartigimod, and incidence of antibodies and NAb produced against rHuPH20. Data for efgartigimod serum concentrations will be summarized. Total IgG serum levels and autoantibody data will be summarized in absolute values, change from baseline, and percent reduction from baseline over time. Population PK/PD analysis may be performed based on the PK and PD data and reported separately.

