4.1.3.2 Presentation of Results

1) Summary statistics on NCOD and (non-normalized) cumulative OCS dose (COD) will be provided.

An ANCOVA model with factors for treatment and the stratification variables will be applied on NCOD. Least square (LS) means and standard error (SE) with 95% 2-sided CI for placebo and efgartigimod will be reported, along with the difference in LS means of IMP vs placebo (with SE), 95% 2-sided CI, and 2-sided p-value.

The supplementary analysis (using the treatment policy strategy) will be analysed in a similar way (descriptive statistics and ANCOVA). This supplementary estimator is not considered in the family wise alpha control.

2) Frequency tabulations will be provided for the percentages of participants within each outcome of IGA-BP per analysis visit. Additionally cumulative percentages (starting with the best outcome result) will be calculated. For participants who received rescue therapy, only assessments prior to or on the start date of rescue therapy will be considered.

Frequency tabulations will be provided of the percentage of participants that have achieved IGA-BP score of 0 while receiving efgartigimod PH20 SC or placebo and have been off OCS therapy for ≥8 weeks at week 36.

The same stratified CMH as for the primary endpoint will be performed.

All IGA-BP data will be listed.

[figure not shown]
3) Frequency tabulations will be provided of the percentage of participants that have achieved control of disease activity (CDA) while receiving efgartigimod PH20 SC or placebo and remain free of relapse through week 36.

The same stratified CMH as for the primary endpoint will be performed.

4) Frequency tabulations will be provided of the percentage of participants that have achieved CR while receiving efgartigimod PH20 SC or placebo and while receiving minimal OCS therapy for ≥8 weeks (CRmin) at week 36.

The same stratified CMH as for the primary endpoint will be performed.

5) Descriptive statistics will present the actual values and changes from baseline of the itch NRS 24-hour average score per analysis visit. For participants who received

rescue therapy, only assessments prior to or on the start date of rescue therapy will be considered.

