Descriptive statistics on absolute values and changes from baseline for EQ-5D-5L VAS score, DLQI score and Total ABQOL score will be calculated per time point.

The same MMRM model as for the itch NRS score will be applied to analyse these changes from baseline but using a standard unstructured covariance matrix (UN) since there are only 3 post-baseline visits during the treatment-phase.

17) C-GTI: Composite Glucocorticoid Toxicity Index comprises the Aggregate Improvement Score (AIS) and the Cumulative Worsening Score (CWS) (health impact of GC) and is derived at baseline, Week 12, Week 26, and Week 36/ETD/ESD. AIS and CWS are calculated for the first 12 weeks, 26 weeks, and 36 weeks period and overall (period till last post-baseline assessment). Details of AIS and CWS derivations are specified in appendix 9.2.

A 'treatment policy' approach will be applied by ignoring ICEs. For participants who received rescue therapy, only assessments prior to or on the start date of rescue therapy will be considered.

Descriptive statistics will be provided for the C-GTI scores AIS and CWS; treatment groups will be compared at each visit using the same ANCOVA model as for the NCOD analysis. C-GTI will be analysed on complete cases: i.e., participants with C-GTI assessment at baseline and at least one post-baseline visit. Participants where first post-baseline GTI improvements/worsening have not been obtained with respect to the baseline moment but with respect to a later moment (i.e., no GTI assessment at baseline visit) are excluded from analyses and are only listed.

Kaplan-Meier curves will be created for all 'time to event' endpoints.

[figure not shown]
Separate listings will be created for all 'time to event' endpoints, for lesion assessments, for BPDAI assessments and scores, for ABQOL, EQ-5D-5L and DLQI data, for calculated C-GTI scores and for complementary GTI specific list (GTI-SL).

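### The SAP replaces the protocol's repeated-measures model for C-GTI with a per-visit ANCOVA, does not declare the change, and leaves the week 36 score after rescue undefined

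*SAP*

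**What the plan says.** Protocol 9.3.3.2: "All continuous secondary endpoints (such as the C-GTI and QoL instruments) will be analyzed using a mixed-effect model for repeated measures".

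SAP 4.1.4 item 17, on AIS and CWS: "treatment groups will be compared at each visit using the same ANCOVA model as for the NCOD analysis". The model referred to is in SAP 4.1.3.2: "An ANCOVA model with factors for treatment and the stratification variables will be applied on NCOD". It has no visit term and no within-participant correlation. SAP Table 4 also lists ANCOVA for C-GTI, so the choice is deliberate.

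The QoL scores, which the protocol pairs with the C-GTI, keep the MMRM in SAP 4.1.4, "using a standard unstructured covariance matrix (UN) since there are only 3 post-baseline visits during the treatment-phase". Both instruments are assessed at baseline and weeks 12, 26 and 36.

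Three further rules in item 17 matter:
- On intercurrent events: "A 'treatment policy' approach will be applied by ignoring ICEs".
- On rescue: "For participants who received rescue therapy, only assessments prior to or on the start date of rescue therapy will be considered".
- On the population: "C-GTI will be analysed on complete cases: i.e., participants with C-GTI assessment at baseline and at least one post-baseline visit".

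One of the three events in protocol 6.8.3 that stop IMP and permit rescue is: "The participant presents with steroid toxicity (or any severe AE determined by the investigator to be related to OCS therapy".

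SAP 6.1 declares three departures from the protocol: the body weight used in NCOD, the definitions of intercurrent medication, and death as an intercurrent event. SAP 6.2 and 6.3 are marked as not applicable. The C-GTI model appears in none of them.

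**The concern.** The SAP contradicts the protocol on a named instrument and gives no reason. Its ground for an unstructured MMRM on the QoL scores, few post-baseline visits, applies equally to the C-GTI.

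The choice matters because of the rescue rule. Participants who stop IMP are encouraged to stay to week 36, but GTI assessments made after rescue starts are not used. A per-visit model at week 36 sees only participants with a week 36 score. If rescued participants have none, their week 12 and 26 scores play no part in that comparison, and they are partly selected on the outcome being measured. With more rescue on placebo, the week 36 difference would tend towards zero. The objective at stake is the reduction of glucocorticoid toxicity. The label for intercurrent events does not repair this, because rescue has its own exclusion rule.

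**Working it through.** The plan states no C-GTI figure, so there is none to reproduce. The first two steps are readings of the text; the third is illustrative.

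**Step 1: the model.** Protocol: repeated-measures mixed model. SAP: ANCOVA at each visit, treatment and strata. Declared in SAP 6.1: no. With three post-baseline visits an unstructured covariance needs 3 × 4 / 2 = 6 parameters, so size is no obstacle.

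**Step 2: what happens to a participant rescued after week 12 or week 26.** The SAP allows two readings.
- *No week 36 score is derived.* The week 36 ANCOVA omits the participant; an MMRM would use the earlier scores.
- *A week 36 score is derived.* SAP 9.2.1 scores a missing evaluation as no change with weight 0, and SAP 9.2.2 sums items over all post-baseline time points up to week 36. If this covers a wholly missing or excluded assessment, the score is frozen at its pre-rescue value. Nobody is dropped and the choice of model makes little difference, but later toxicity is counted as nil.

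Item 17 requires a baseline and at least one post-baseline assessment, not a score at the visit analysed, so it does not settle the matter.

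**Step 3: possible size under the first reading.** All inputs are assumed. Scores have unit SD. The true differences at weeks 12, 26 and 36 are -0.40/3, -0.80/3 and -0.40 SD. The correlation is ρ between adjacent visits and ρ^1.5 between the first and third. The probability of rescue before the next visit is 1/(1 + exp(-(c + 1.5s))), with c set so that 10%, 20% or 40% are rescued before week 36. Here s is either the last recorded score or the upcoming, unrecorded one. The calculation used 400,000 simulated participants; the per-visit estimate is the difference in observed means, without strata.

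| Rescue follows | Rescued, placebo / efgartigimod | ρ | Per-visit estimate | MMRM estimate |
|---|---|---|---|---|
| recorded score | 11% / 9% | 0.5; 0.7 | -0.389; -0.382 | -0.401; -0.398 |
| recorded score | 22% / 18% | 0.5; 0.7 | -0.376; -0.373 | -0.397; -0.401 |
| recorded score | 43% / 37% | 0.5; 0.7 | -0.364; -0.352 | -0.396; -0.396 |
| unrecorded score | 12% / 8% | 0.5; 0.7 | -0.362; -0.360 | -0.372; -0.379 |
| unrecorded score | 23% / 17% | 0.5; 0.7 | -0.339; -0.331 | -0.352; -0.361 |
| unrecorded score | 45% / 35% | 0.5; 0.7 | -0.315; -0.305 | -0.332; -0.345 |

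Shrinkage is 1 - |estimate|/0.40. Per visit it runs from 1 - 0.389/0.40 = 3% to 1 - 0.305/0.40 = 24%. For MMRM it is 0% to 1% when rescue follows recorded scores, and 5% (1 - 0.379/0.40) to 17% (1 - 0.332/0.40) when it does not.

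A second set of assumptions used 60 per arm, a true week 36 CWS difference of about -17, and rescue following recorded scores only. Rescue of 25% on placebo and 10% on efgartigimod gave per-visit estimates of -11.9 to -7.9, a shrinkage of 30% to 54%; MMRM gave -16.6 to -17.2. Rescue of 30% and 10% gave -11.3 to -5.3, a shrinkage of 34% to 69%. Equal rescue of 20% gave a bias of only 0.4 to 1.0. The result therefore depends heavily on the assumed imbalance between arms.

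**The case against.** The case for leaving the ANCOVA alone has substance.

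- **Rescue is optional.** Protocol 6.8.3 says participants may start it. Those who stop IMP for steroid toxicity without rescue keep their later scores. This stands.
- **Some toxicity before rescue is kept.** GTI is scheduled at the ETD visit, where rescue may begin, and assessments on or before the start date count. Item 17 also derives an overall score to the last assessment. This largely stands. However, the overall score gives rescued participants less time to accumulate worsening. Item 17 labels its last time point week 36/ETD/ESD while SAP 2.2.4 allocates assessments by study day, so it is unclear that an ETD score serves as a week 36 score.
- **MMRM cannot use scores that do not exist.** Under protocol 6.8.1.3, initial treatment failure is reached after roughly 4 to 7 weeks, before the week 12 GTI. Rescue driven by unrecorded toxicity also leaves bias. Both points stand and limit the benefit.
- **The QoL model does not transfer unchanged.** It has a baseline-by-visit term, whereas AIS and CWS are already changes accumulated from baseline. This stands and is met by omitting the term.
- **The endpoint is descriptive and any bias of this kind is conservative.** This stands as to consequence. The NCOD model still reports a difference with a 95% CI and p-value, so a between-arm result will be read.

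A reader might infer that the week 36 comparison drops the most steroid-toxic participants. The documents do not establish that: rescue is optional, two of its three triggers are not toxicity, and the SAP does not say whether a rescued participant lacks a week 36 score.

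**Conclusion.** The contradiction is established from the text: MMRM in the protocol, per-visit ANCOVA in the SAP, and no declaration. The bias is conditional. It arises if rescued participants have no derived week 36 score, and it works towards zero if rescue is more frequent on placebo. Its size cannot be stated, because the documents give no C-GTI effect, SD, correlation or rescue rate. The figures above, from 3% to 24% in one set of assumptions and 30% to 69% in another with strongly unequal rescue, illustrate direction and sensitivity and are not estimates for this trial.

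It would also be too strong to infer that MMRM cures the problem: it corrects for rescue that follows recorded scores and only partly for rescue that follows unrecorded toxicity. Nor is any confirmatory conclusion at risk, since the C-GTI lies outside alpha control. The change is still worth making, because it restores what the protocol specifies, costs little, and is less biased when rescue depends on recorded scores.

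**What to change.** 1. In SAP 4.1.4 item 17 and Table 4, analyse AIS and CWS at weeks 12, 26 and 36 with an unstructured MMRM containing treatment by visit and the two stratification factors. Omit the baseline-by-visit term.
2. Keep the per-visit ANCOVA and the overall last-assessment score as supportive. If the ANCOVA is instead to remain the main analysis, declare and justify it in SAP 6.1.
3. In SAP 9.2, state whether a week 36 score is derived after rescue or when the whole assessment is missing, and whether the weight-0 rule applies then. The MMRM gains anything only where such scores are left missing.

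The cost is SAP wording and a small adaptation of the QoL MMRM code. No new data are needed.
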